4.1 Screening/Enrolment period

Procedures will be performed according to the study plan (see [Table 2](#) and [Table 3](#)).

At screening, consenting patients are assessed to ensure that they meet eligibility criteria. Patients who do not meet these criteria must not be randomised in the study.

All patients will be required to provide consent to supply a suitable FFPE prepared tumour sample (that meets the tissue specifications outlined in the Laboratory Manual) for testing on the Lynparza HRR assay for entry into this study. This consent is included in the screening patient informed consent form.

4.2 Treatment period

Procedures during treatment and on study treatment discontinuation will be performed according to Study Plan (see [Table 4](#) and [Table 5](#)).

One cycle comprises 28 days for the olaparib monotherapy and ceralasertib+olaparib treatment arms. For the AZD1775+olaparib treatment arm (olaparib monotherapy only following the closure of this treatment arm in April 2019), one cycle comprises 21 days. Unless otherwise specified, procedures should be conducted on the scheduled day (± 3 days). This excludes the visits on Day 1 and Day 7 of Cycle 1 for olaparib monotherapy and ceralasertib+olaparib treatment arms and Day 1 and Day 10 of Cycle 1 for the AZD1775+olaparib treatment arm, where all specified procedures should be carried out the same day.

4.3 Follow-up period

Assessments at the end of the treatment period will be conducted 30 days (+7 days) after the last dose of study treatment according to Study Plan (see [Table 4](#) and [Table 5](#)).

Survival follow-up will be conducted approximately every 8 weeks (± 7 days) after the 30-day follow-up visit according to Study Plan (see [Table 4](#) and [Table 5](#)).

5. STUDY ASSESSMENTS

The Clinical Database will be used for data collection and query handling. The Investigator will ensure that data are recorded on the eCRFs as specified in the Clinical Study Protocol and in accordance with the instructions provided.

The Investigator ensures the accuracy, completeness, and timeliness of the data recorded and of the provision of answers to data queries according to the Clinical Study Agreement (CSA). The Investigator will sign the completed eCRFs. A copy of the completed eCRFs will be archived at the study site. For details on keeping source data refer to the CSA (see [Section 9.2.1](#)).

5.1 Efficacy assessments

5.1.1 CT and MRI scans; Tumour assessments (RECIST 1.1)

Following the baseline assessment, subsequent tumour assessments according to RECIST 1.1 should be performed every 8 weeks (± 1 week) for the first 72 weeks and then every 12 weeks (± 1 week) thereafter, relative to the date of randomisation and irrespective of treatment decisions, up to objective disease progression by RECIST 1.1.

The imaging modalities used for RECIST 1.1 assessment will be CT scans of the chest, abdomen and pelvis (or MRI where CT is contraindicated) with other regions as clinically indicated for the assessment of disease. Brain CT scan/MRI at baseline should be done for patients with known history of brain metastatic disease. Any other sites at which new disease is suspected should also be appropriately imaged. The methods of assessment of tumour burden used at baseline must be used at each subsequent follow-up assessment.

Radiological examinations performed in the conduct of this study should be retained at site as source data.

Coded copies of all scans, regardless of modality, are to be sent to an AstraZeneca appointed CRO for BICR.

All treatment decisions will be based on site assessment of scans. After the primary PFS analysis for each of the strata, central review of scans will no longer be required for that stratum and Investigators will be advised when to stop sending copies of the scans to the CRO conducting the central review. Patients who are determined to have progressed according to RECIST 1.1 criteria by the Investigator will have scans centrally reviewed for confirmation of objective disease progression. If disease progression is not confirmed at central review an additional RECIST 1.1 assessment may be requested preferably at the next scheduled RECIST 1.1 visit, if the central assessment is available in an appropriate timeframe.

It is important to follow the assessment schedule as closely as possible. If scans are performed outside of scheduled visit ± 1 week window interval and the patient has not progressed, every attempt should be made to perform the subsequent scans at their scheduled time points. Patients will be evaluated until objective radiological disease progression by RECIST 1.1 as per the study schedule (see [Table 3](#), and [Table 4](#) and [Table 5](#)), and then followed for survival, regardless of whether study treatment is discontinued or delayed and/or protocol violations, unless they withdraw consent.

5.1.2 Tumour evaluation

RECIST 1.1 criteria will be used to assess patient response to treatment by determining PFS times and ORRs as appropriate to study endpoints. The RECIST 1.1 guidelines for measurable, non measurable, target and non target lesions and the objective tumour response criteria (CR, PR, SD or progressive disease [PD]) are presented in [Appendix F](#).

The methods of assessment of tumour burden used at baseline - CT or MRI scans of chest, abdomen, and pelvis (as well as brain CT scan/MRI for patients with known history of brain metastatic disease) must be used at each subsequent follow-up assessment. Any other areas of disease involvement should be additionally imaged based on the signs and symptoms of individual patients.

Following the baseline assessment, efficacy for all patients will be assessed by objective tumour assessments every 8 weeks until Week 72 and every 12 weeks thereafter until objective disease progression as defined by RECIST 1.1. Any other sites at which new disease is suspected should also be appropriately imaged.

If a patient discontinues treatment (and/or receives a subsequent cancer therapy) prior to progression then the patient should still continue to be followed until objective disease progression as defined by RECIST 1.1.

Categorisation of objective tumour response assessment will be based on the RECIST 1.1 criteria of response: CR, PR, SD and PD. Target lesion (TL) progression will be calculated in comparison to when the tumour burden was at a minimum (ie, smallest sum of diameters previously recorded on study). In the absence of progression, tumour response (CR, PR, SD) will be calculated in comparison to the baseline tumour measurements obtained before starting treatment.

Following progression, patients should continue to be followed up for survival approximately every 8 weeks as outlined in the study plan.

It is important to follow the assessment schedule as closely as possible. Please refer to the study plan in [Table 3](#), [Table 4](#) and [Table 5](#).

Following the final PFS analysis data cut off for each stratum (either non HRR*m*, BRC*Am* and/or non BRC*Am* HRR*m*) objective tumour assessments should be performed as per the study schedule (see [Table 3](#), [Table 4](#) and [Table 5](#)) for patients continuing on treatment and recorded in the patient notes **but not** recorded in the eCRF.

Central reading of scans

An independent review of all scans used in the assessment of tumours using RECIST 1.1 will be conducted. All imaging assessments including unscheduled visit scans will be collected on an ongoing basis and sent to an AstraZeneca appointed CRO for central analysis up until the data cut off for the final analysis for PFS in an individual stratum. The management of patients will be based solely upon the results of the RECIST 1.1 assessment conducted by the Investigator.

The interim and primary PFS analysis for this study will be based on the BICR of the radiological scans.

5.2 Safety assessments

5.2.1 Laboratory safety assessments

All laboratory assessments described below will be performed at the local laboratories. Blood and urine samples for determination of clinical chemistry, haematology, coagulation, and urinalysis will be taken at the times indicated in the Study Schedule (see [Table 3](#), [Table 4](#) and [Table 5](#)).

Following the final PFS analysis data cut off for each stratum (either non HRR*m*, BRC*Am* and/or non BRC*Am* HRR*m*) laboratory assessment samples should be taken as per the study schedule (see [Table 3](#), [Table 4](#) and [Table 5](#)) for patients continuing on treatment, recorded both in the patient notes and the eCRF.

Additional safety samples may be collected if clinically indicated at the discretion of the Investigator. The date, time of collection and results (values, units and reference ranges) will be recorded on the appropriate eCRF.

The clinical chemistry, haematology and urinalysis will be performed at a local laboratory at or near to the Investigator site. Sample tubes and sample sizes may vary depending on laboratory method used and routine practice at the site.

The following laboratory variables will be measured ([Table 7](#)):

Table 7 Laboratory safety variables

Haematology/Haemostasis (whole blood)	Clinical Chemistry (serum or plasma)
B-Haemoglobin (Hb)	S/P-Creatinine
B-Leukocyte count	S/P-Bilirubin, total
B-Absolute neutrophil count	S/P-Alkaline phosphatase (ALP)
B-Absolute lymphocyte count	S/P-Aspartate transaminase (AST)
B-Platelet count	S/P-Alanine transaminase (ALT)
B-Mean Cell Volume (MCV)	S/P-Albumin
	S/P-Calcium
Urinalysis (dipstick)	S/P-Potassium
U-Hb or Erythrocytes or Blood	S/P-Sodium
U-Protein or Albumin	S/P-Urea or blood urea nitrogen (BUN)
U-Glucose	S/P-Total Protein
	C-reactive protein
Coagulation tests	
Pregnancy tests	

The Investigator should make an assessment of the available results with regard to clinically relevant abnormalities. The laboratory results should be retained at centre as source data for laboratory variables. For information on how AEs based on laboratory tests should be recorded and reported, see Section 6.3.

In case a patient shows an AST **or** ALT ≥ 3 x ULN **or** total bilirubin ≥ 2 x ULN please refer to [Appendix D](#) ‘Actions required in cases of combined increase of Aminotransferase and Total Bilirubin – Hy’s Law’, for further instructions.

5.2.1.1 Coagulation

Coagulation tests should be performed at screening and subsequently if clinically indicated.

- Activated partial thromboplastin time will be performed at screening and sequentially if clinically indicated
- International normalised ratio (INR) will be performed at screening and sequentially if clinically indicated. Patients taking warfarin may participate in this study; however, it is recommended that INR be monitored carefully at least once per week for the first month, then monthly if the INR is stable.
- Each coagulation test result will be recorded on the eCRF.

5.2.1.2 Bone marrow or blood cytogenetic samples

Bone marrow or blood cytogenetic samples may be collected for patients with prolonged haematological toxicities as defined in Section 6.8.1.

Bone marrow analysis should include an aspirate for cellular morphology, cytogenetic analysis and flow cytometry, and a core biopsy for bone marrow cellularity. If it is not possible to conduct cytogenetic analysis or flow cytometry on the bone marrow aspirate, then attempts should be made to carry out the tests on a blood sample. Full reports must be provided by the Investigator for documentation on the Patient Safety database. These data are not required to be entered into the eCRF.

5.2.2 Physical examination

A complete physical examination including determination of weight and height will be performed and include an assessment of the following: general appearance, respiratory, cardiovascular, abdomen skin, head and neck (including ears, eyes, nose and throat), lymph nodes, thyroid, abdomen, musculo-skeletal (including spine and extremities) and neurological systems.

Physical examinations will be performed at screening, prior to dosing on Day 1 of each treatment cycle, at study treatment discontinuation, and at the 30-day follow-up (see [Table 3](#), and [Table 4](#) and [Table 5](#)).

Following the final PFS analysis data cut off for each stratum (either non HRR*m*, BRC*Am* and/or non BRC*Am* HRR*m*) a complete physical examination should be performed as per the study schedule (see [Table 3](#), [Table 4](#) and [Table 5](#)) for patients continuing on treatment and recorded in the patient notes **but not** recorded in the eCRF.

Clinically relevant worsening of physical examination findings will be recorded as AEs for all patients up until the final analysis. For information on recording of AEs see [Section 6.3](#).

5.2.3 ECG

5.2.3.1 Resting 12-lead ECG

Triplicate ECG recordings are required within 7 days prior to starting study treatment (i.e, during screening) in all patients. A single ECG is required at subsequent timepoints for patients in the olaparib monotherapy or ceralasertib+olaparib arms, and triplicate ECGs for patients in the AZD1775+olaparib treatment arm (**from April 2019 triplicate ECG no longer applies to patients who have discontinued AZD1775 but single ECGs should be taken at the stated timepoints**). ECG recordings are required on Days 1, 7, and 15 of Cycle 1 (Days 1, 10 and 15 of Cycle 1 for the AZD1775+Olaparib arm), on Day 1 of each subsequent cycle (prior to dosing), at study treatment discontinuation, and at the 30-day follow-up (see [Table 3](#), and [Table 4](#) and [Table 5](#)).

Following the final analysis for PFS data cut off for a stratum (either non HRR*m*, BRC*Am* or non BRC*Am* HRR*m*), for patients remaining on treatment, ECG recordings should be taken as per the study schedule (see [Table 3](#), [Table 4](#) and [Table 5](#)) and recorded in the patient notes **but not** recorded in the eCRF.

Triplicate ECG recordings should be taken within an approximate 5-minute period. Additional ECGs may be taken at any other time the Investigator deems necessary for safety during the administration period. The patients will rest for at least 10 minutes before the start of each recording and they must be in the same supine body position (45 degree flexion in the hip and feet not in contact with the footboard) at the recording time point. The Investigator or designated physician will review the paper copies of each of the timed 12-lead ECGs on each of the study days when they are collected.

ECGs will be recorded at 25 mm/sec. All ECGs should be assessed by the Investigator as to whether they are clinically significantly abnormal / not clinically significantly abnormal. If there is a clinically significant abnormal finding, the Investigator will record it as an AE on the eCRF for all patients up until the final analysis. For information on recording of AEs see [Section 6.3](#). The original ECG traces must be stored in the patient medical record as source data.

Attention should be paid to any detected increases in QTc interval. Patients who develop a single resting value of QTc interval of >450 msec/male and >470 msec/female or a shift from baseline of 60ms should stop taking the study treatment. Dosing can be resumed at a reduced dose after return of the resting QTc interval to pre-treatment status has been confirmed and

correction of possible electrolyte imbalance has been made. Monitoring of QTc, checking and correction of abnormal electrolyte levels and renal function are advised, especially in case of severe/prolonged diarrhoea. If QTc increases markedly from baseline, but stays below the above limits, a cardiologist's advice should be sought. The concomitant use of ondansetron (known to prolong the QTc interval in rare cases, per labelling) should be taken into account when interpreting QTc changes.

5.2.4 Vital signs

Vital signs will be assessed at screening and, if clinically indicated, on Day 1 of each treatment cycle. If the assessments were done within 7 days before starting study treatment, they do not have to be repeated on day 1 of study treatment within the respective treatment cycles unless the Investigator believes results have changed significantly. Vital signs will also be assessed at the 30-day follow-up and at discontinuation (see [Table 3](#), [Table 4](#) and [Table 5](#)).

Following the final analysis for PFS data cut off for a stratum (either non HRRm, *BRCAm* and/or non *BRCAm* HRRm) for patients remaining on treatment vital signs will be assessed as per the study schedule (see [Table 3](#), [Table 4](#) and [Table 5](#)) and recorded in the patient notes **but not** recorded in the eCRF.

Weight will be assessed as part of the physical examination (see [Section 5.2.2](#)).

Any changes in vital signs should be recorded as an AE, if applicable, for all patients up until the final analysis. For information on how AEs based on changes in vital signs should be recorded and reported, see [Section 6.3](#).

5.2.4.1 Pulse and blood pressure

Blood pressure and pulse will be assessed according to the Study Schedule (see [Table 3](#), and [Table 4](#) and [Table 5](#)) and as clinically indicated at any other time.

Blood pressure and pulse rate will be measured preferably using a semi-automatic BP recording device with an appropriate cuff size after 10 minutes rest.

The date of collection and measurement will be recorded on the appropriate eCRF.

Following the final PFS analysis data cut off for a stratum (either non HRRm, *BRCAm* and/or non *BRCAm* HRRm), for patients remaining on treatment, blood pressure and pulse should be measured as per the study schedule (see [Table 3](#), [Table 4](#) and [Table 5](#)) and recorded in the patient notes **but not** recorded in the eCRF.

5.2.4.2 Body temperature

Body temperature will be measured in degrees Celsius according to local practice according to the Study Schedule (see [Table 3](#), [Table 4](#) and [Table 5](#)) and as clinically indicated at any other time.

The date of collection and measurement will be recorded on the appropriate eCRF.

Following the final PFS analysis data cut off for a stratum (either non HRRm, *BRCAm* and/or non *BRCAm* HRRm), for patients remaining on treatment, body temperature should be measured as per the study schedule (see [Table 3](#), [Table 4](#) and [Table 5](#)) and recorded in the patient notes **but not** recorded in the eCRF.

5.2.5 Other safety assessments

5.2.5.1 Serum or urine pregnancy test

Pregnancy tests on blood or urine samples will be performed for women of childbearing potential at Screening Part 1 (see [Table 2](#)), within 28 days prior to the start of study treatment on Day 1 of the study prior to commencing treatment, at the time points shown in [Table 4](#) and [Table 5](#) during study treatment and at the 30-day follow-up visit. Tests will be performed by the hospital's local laboratory (urine pregnancy dipstick is not permitted). If results are positive the patient is ineligible/must be discontinued from study treatment immediately.

5.3 Other assessments

5.3.1 CCI [REDACTED]

5.3.1.1 CCI [REDACTED]

In this study, patients will CCI [REDACTED] CCI [REDACTED] (see Section 5.3.1.2).

CCI [REDACTED]

CCI [REDACTED]

CCI [REDACTED]

- [REDACTED]

- [REDACTED]

- [REDACTED]

- **CCI** [Redacted]
- **CCI** [Redacted]
- **CCI** [Redacted]

CCI [Redacted]

[Redacted]

[Redacted]

5.4 Pharmacokinetics

The following PK sampling will be performed on Cycle 1 cross the 3 treatment arms in all patients (see below).

Olaparib arm

	Day 1	Day 7
pre-dose		✓
0.5 hour (± 0.5 hour)		✓
2 hours (± 1 hour)	✓	✓
4.5 hours (± 1.5 hour)	✓	✓
9 hours (± 3 hours)	✓	✓

Ceralasertib and olaparib arm

	Day 1	Day 7
pre-dose		✓
0.5 hour (± 0.5 hour)		✓
2 hours (± 1 hour)	✓	✓
4.5 hours (± 1.5 hour)	✓	✓
9 hours (± 3 hours)	✓	✓

AZD1775 and olaparib arm - this treatment arm was closed following the ISRC meeting on the 17 April 2019

	Day 1	Day 10
pre-dose		✓
0.5 hour (± 0.5 hour)		✓
2 hours (± 1 hour)	✓	✓
4.5 hours (± 1.5 hour)	✓	✓
9 hours (± 3 hours)	✓	✓

For all treatment arms, patients should be instructed to fast and hold their morning dose of AZD1775/olaparib on any day PK sampling is scheduled so it may have timed administration in the clinic. The date and actual time of the PK sample is to be recorded in the medical records and eCRF.

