- g Pregnancy tests using blood or urine samples will be performed for women of childbearing potential within 28 days prior to the start of study treatment, on Day 1 of the study prior to commencing treatment, on Day 1 of each subsequent treatment cycle and at the follow-up visit 30 days after last dose of study medication. If results are positive, the patient must be discontinued from the study treatment immediately. Tests will be performed by the hospital's local laboratory.
- h When an AE for nausea and vomiting occurs, an additional eCRF will require completion. All ongoing AEs/SAEs and any new AEs/SAEs identified during the 30 calendar day's follow-up period after last dose of study medication must be followed to resolution.
- i To be completed every 8 weeks (± 1 week) until discontinuation of study treatment. Following the data cut off for the final analysis for PFS patients will no longer be required to complete the **CCI**.
- j Only at progression.
- k A common PK time window will be used for olaparib and ceralasertib in all patients: Cycle 1 Day 1: 2 hours (± 1 hour), 4.5 hours (± 1.5 hour) and 9 hours (± 3 hours), Cycle 1 Day 7: pre-dose, 0.5hour (± 0.5 hour), 2 hours (± 1 hour), 4.5 hours (± 1.5 hours) and 9 hours (± 3 hour).
- l The pharmacogenetic blood sample can be obtained either at the first treatment visit or after randomisation
- m If a patient has experienced a Grade 3/4 neutropenia, G4 thrombocytopenia, or a dose interruption due to haematological toxicity in a prior cycle, unscheduled Day 8 and Day 15 complete blood counts are required in subsequent treatment cycles. If no further events are experienced in the subsequent 3 consecutive cycles, then the Day 15 CBC visit can be stopped.

* Please note that the cycle length for olaparib monotherapy and ceralasertib+olaparib treatment arms will be 28 days.
PBMC=peripheral blood mononuclear cell

Table 5 AZD1775+Olaparib Schedule of Assessments (applies to Patients Randomised to this Treatment Arm who, after April 2019, continue on Olaparib monotherapy)

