7.2 Dose and treatment regimens

Olaparib

Olaparib tablets will be packed in high-density polyethylene bottles with child-resistant closures and will be available as film coated tablets containing 100 mg or 150 mg of olaparib. Each dosing container will contain sufficient medication for at least 28 days plus coverage. Olaparib will be dispensed to patients on Day 1 of every cycle until the patient completes the study, withdraws from the study or closure of the study. Medication accountability should be completed at Day 1 of each Cycle (Table 4 and Table 5).

In the olaparib monotherapy treatment arm as well as in the ceralasertib+olaparib treatment arm, patients will be administered olaparib bd at 300 mg continually. Two (2) 150 mg olaparib tablets should be taken at the same time each day, approximately 12 hours apart with one glass of water (approximately 250 mL). In the AZD1775+olaparib treatment arm, patients will be given olaparib 200 mg bd (2 x 100 mg tablets twice a day). Following the ISRC meeting on 17 April 2019 a recommendation was made to close the AZD1775+olaparib treatment arm across all biomarker strata and that patients currently receiving treatment with AZD177+olaparib treatment be offered the opportunity to continue treatment of olaparib monotherapy at the approved dose 300 mg bd at the patient's next treatment cycle.

Olaparib tablets should be swallowed whole and not chewed, crushed, dissolved or divided. The tablets can be taken with or without food. If vomiting occurs shortly after the olaparib tablets are swallowed, the dose should only be replaced if all of the intact tablets can be seen and counted. Should any patient enrolled on the study miss a scheduled dose for whatever reason (eg, as a result of forgetting to take the tablets or vomiting), the patient will be allowed to take the scheduled dose up to a maximum of 2 hours after that scheduled dose time. If greater than 2 hours after the scheduled dose time, the missed dose is not to be taken and the patient should take their allotted dose at the next scheduled time.

Ceralasertib

Ceralasertib will be supplied as 20 mg, 80 mg, or 100 mg film coated tablets. Patients will be administered ceralasertib od at 160 mg from Day 1 to Day 7 (inclusive) of every 28-day cycle. A total of 160 mg of ceralasertib tablets should be taken at the same time on each day of dosing with approximately 250 mL of water. When ceralasertib is taken in combination with

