olaparib, it is advised that it is taken at the same time of day. Ceralasertib tablets should be swallowed whole and not chewed, crushed, dissolved or divided. Patients must fast (water to drink only) from at least 2 hours prior to taking their ceralasertib dose to at least 1 hour post-dose for all doses. No fasting restrictions apply when olaparib is taken on its own.

If vomiting occurs shortly after the ceralasertib tablets are swallowed, the patient should be instructed not to retake the dose, but wait until the next scheduled dose of ceralasertib. If no dose is scheduled for the following day, the dose will not be made up. If a patient misses a scheduled dose (e.g. as a result of forgetting to take the tablets), the patient will be allowed to take the scheduled dose up to a maximum of 2 hours after that scheduled dose time. If greater than 2 hours after the scheduled dose time, the missed dose is not to be taken and the patient should take their allotted dose at the next scheduled time.

Medication accountability should be completed at Day 1 of each Cycle (Table 4 and Table 5).

AZD1775 - this treatment arm was closed following the ISRC meeting on the 17 April 2019

AZD1775 will be supplied as capsules containing 25 mg, 50 mg, 75 mg, 100 mg, or 200 mg of drug substance. AZD1775 will be provided by AstraZeneca. Patients will be administered AZD1775 bd at 150mg from Day 1 to Day 3 (inclusive) and Day 8 to Day 10 (inclusive) of every 21 day cycle. AZD1775 capsules should be swallowed whole and not chewed, crushed, dissolved or divided. AZD1775 should be taken with approximately 250 mL of water approximately 2 hours before or 2 hours after food. These restrictions should be applied to the AZD1775+olaparib treatment arm.

If a patient misses one of the two daily doses according to schedule, the dose should be taken as soon as possible, but not more than 6 hours after the missed dose was scheduled. If greater than 6 hours, the missed dose should be skipped and the patient should take the next dose when scheduled.

If vomiting occurs after a patient takes the AZD1775 dose, the patient should be instructed not to retake the dose, but to wait until the next scheduled dose of AZD1775. If no dose is scheduled for the following day, the dose will not be made up. If vomiting persists, the patient should contact the Investigator.

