3.6 Secondary outcome measures (derivation of PK variables)

The minimum concentrations at steady state ($C_{\min ss}$) will be derived from the drug concentration data for Olaparib, AZD6738 and AZD1775, and provided to PAREXEL Biostatistics.

Given the sparse PK schedule, other PK parameters will be derived using population PK modelling described in a separate analysis plan. The results of any such analyses will be reported separately from the CSR.

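### The PK-day hold instruction in Protocol 5.4 covers all arms but omits ceralasertib, so the only sample that can give ceralasertib Cmin,ss is not secured as pre-dose

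*Protocol*

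**What the plan says.** Protocol 5.4 gives the ceralasertib arm its own sampling table: three post-dose samples on Cycle 1 Day 1, and a pre-dose sample plus four post-dose samples on Day 7, the last at "9 hours (± 3 hours"). Table 4 footnote k repeats the Day 7 schedule ("Cycle 1 Day 7: pre-dose") and ties the two drugs together: "A common PK time window will be used for olaparib and ceralasertib in all patients".

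Under those tables, 5.4 sets the handling rule for every arm: "patients should be instructed to fast and hold their morning dose of AZD1775/olaparib on any day PK sampling is scheduled". The aim it gives is dosing at a known time during the visit. It then asks for the date and actual time of the PK sample. It does not mention the time of the dose.

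On dosing, Protocol 7.2 says "Patients will be administered ceralasertib od at 160 mg from Day 1 to Day 7 (inclusive) of every 28-day cycle". When ceralasertib is combined with olaparib, 7.2 adds that "it is advised that it is taken at the same time of day".

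Protocol 2.2 gives Cmin,ss as the one outcome measure for the secondary objective on exposure to the three drugs. SAP 3.6 says that Cmin,ss "will be derived from the drug concentration data for Olaparib, AZD6738 and AZD1775". SAP 4.2.9 summarises it, and the SAP's list of outputs gives ceralasertib (AZD6738) Cmin,ss its own table, T 11.2.7.5.

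**The concern.** The hold instruction makes a sample labelled pre-dose actually pre-dose. As written it names olaparib and a drug that Protocol 7.1 says is no longer supplied. It leaves out the one investigational combination drug still being given. Patients self-administer (Protocol 7.5), so a site that follows the sentence literally tells a ceralasertib patient to hold olaparib and says nothing about the ceralasertib tablets. The instruction to fast does not close the gap, because 7.2 has ceralasertib taken fasted in any case.

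If ceralasertib is taken at home on Day 7, the sample labelled pre-dose is a post-dose sample for that drug, and the later Day 7 samples carry the wrong time after dose. Cmin,ss for ceralasertib would then be too high and more variable, and the population PK model could inherit the mistimed records. What is at stake is a descriptive secondary summary. There is no hypothesis test on it and no route to the PFS result.

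**Working it through.** **1. Is Day 7 a ceralasertib dosing day?** Yes. Protocol 7.2 gives once-daily dosing on Days 1 to 7 inclusive, so the dosing interval is 24 h and Day 7 is the last dosing day of the cycle.

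**2. Can another scheduled sample serve as the trough?**
- Day 1 has no pre-dose sample and is not at steady state.
- The latest Day 7 sample is nominally at 9 h with a tolerance of 3 h: 9 + 3 = 12 h after dosing at most.
- 12 / 24 = 0.5, so that sample reaches only half of the dosing interval.

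The Day 7 pre-dose sample is therefore the only scheduled sample that can be a ceralasertib steady-state trough.

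**3. Which text bears on taking ceralasertib before that sample?**

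| Place | What it does | Names ceralasertib or covers it? | A PK-day instruction? |
|---|---|---|---|
| Protocol 5.4 | Hold the morning dose for dosing in clinic | No | Yes |
| Table 4 footnote k | One sampling window for both drugs | Yes | Sets times; no hold |
| Protocol 7.2 | Take the two drugs at one time of day | Yes | No; general advice |
| Protocol 6.8.1.1 and Table 4 footnote c | Blood tests reviewed before dosing; 6.8.1.1 schedules a count on Cycle 1 Day 7 | Yes, through the arm | No; a safety rule |

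No place tells the ceralasertib patient to hold ceralasertib for PK sampling. Day 1 is much less exposed, because Table 4 has the medication dispensed at that visit.

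**4. Direction of the error.** Once some of a home dose has been absorbed, the concentration is above the trough. The bias in Cmin,ss is upward, with extra spread.

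**5. Size: an illustration only.** The documents give neither a ceralasertib half-life nor a home-dosing share. Assume one-compartment decline, absorption complete by 2 h, and a sample 2 h after a home dose.
- Ratio to the true trough: r = 2^((24 − 2)/t½) = 2^(22/t½).
- Geometric mean over all patients, if a share p dosed at home: multiplied by r^p.

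| Assumed t½ | r | p = 0 | p = 0.1 | p = 0.3 |
|---|---|---|---|---|
| 8 h | 6.73 | 1.00 | 1.21 | 1.77 |
| 12 h | 3.56 | 1.00 | 1.14 | 1.46 |
| 20 h | 2.14 | 1.00 | 1.08 | 1.26 |

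The column p = 0 belongs in the table, because the safeguards in step 3 make it plausible. The table shows that a single mistimed sample can be far off. It does not estimate what happened in this trial.

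**The case against.** The strongest reply is that other text already does most of the work. Protocol 6.8.1.1, which covers the ceralasertib combination, schedules a blood count on Cycle 1 Day 7 and requires counts to be reviewed before dosing. Table 4 footnote c says the same of safety bloods generally, and Protocol 4.2 puts all Day 7 procedures on the same day. Read naturally, a dose at home before the visit breaks that rule. A patient who holds olaparib and follows the advice in 7.2 holds both drugs. The common window in footnote k makes sense only if both are dosed together. The intent is clear, and this is a drafting omission. All of that stands, and it lowers the likely frequency. It does not replace the missing instruction: the blood-count rule does not tell the patient to arrive with ceralasertib untaken, and 7.2 is advice.

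The documents do not support three stronger readings that a reader might infer:

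- **That a home dose could never be detected.** The eCRF is not shown. Protocol 7.5 requires administration of all study drugs to be recorded. A diary with dose times is described for all patients, although it sits under the AZD1775 heading in 7.2, so its scope is unclear. Five Day 7 samples with two analytes could also expose a home dose: ceralasertib would already be high when olaparib is still at trough. Any trough check may sit in the derivation step before SAP 4.2.9, which is not described.
- **That Cmin,ss is overstated by some stated percentage.** The illustrative range of 8% to 77% in the working rests wholly on assumed half-lives, timing and shares of 10% to 30%.
- **That Cmin,ss could be limited to time-confirmed samples at little loss.** If dose times were not collected, that rule would remove every ceralasertib sample already taken.

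**Conclusion.** The point holds as an omission in a stated operating rule. The 5.4 sentence claims to cover all arms and does not fit the ceralasertib arm, where it matters for the only sample that can yield ceralasertib Cmin,ss. A home dose before the Day 7 visit is made less likely by other text but is not excluded. If it occurs, ceralasertib Cmin,ss is biased upward, provided the sample follows some absorption of that dose.

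The frequency and the size of the bias cannot be judged from the documents. The primary PFS analysis is unaffected, and so are the olaparib troughs, since olaparib is named in the instruction. The point is worth correcting because the sample cannot be replaced, the measure is the sole one for its objective, and the correction is cheap.

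**What to change.** 1. **Protocol 5.4.** Reconcile the hold sentence with the ceralasertib sampling table in the same section, Table 4 footnote k, 6.8.1.1 and 7.2, so that the Day 7 pre-dose sample is pre-dose for every analyte assayed in that arm.
2. **Data capture.** State that, on PK days, the clock times of the clinic dose and of the preceding dose of each drug are recorded, if the eCRF does not already do this.
3. **SAP 3.6 and 4.2.9.** Exclude from Cmin,ss any sample shown, by recorded times or by the concentration profile, to be post-dose for the drug concerned. Flag samples with unknown dose times and present the summary with and without them, rather than dropping them all.

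**Cost.** A sentence in the protocol, at most two time fields per drug, and a short rule in the SAP; no extra visit or sample. The Cmin,ss table may lose a few samples. The wording change cannot repair samples already taken. The study started in Q1 2018 with 15 months of recruitment assumed, and this protocol version is dated May 2020, so much of the Cycle 1 sampling may be complete. For those patients the SAP rule is the part that helps.
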